3.1.7 Exploratory endpoint(s)

3.1.7.1 Exploratory Efficacy Endpoints

CCI

CCI

3.1.7.2 *Exploratory Biomarkers*

CCI

3.1.8 *Multiplicity*

No multiple testing will be performed in this study.

3.1.9 *Significance testing and estimation*

As this is a descriptive safety and tolerability/efficacy study, no formal statistical testing will be carried out. If p-values are provided, they will only be provided for exploratory purposes only.

3.2 **Analysis methods**

3.2.1 *Safety*

All safety data will be included in the data listings and summary tables will be based on the Safety Analysis Set. Summary tables will be presented by study Part, cohort (part B only), overall Part B and overall.

3.2.1.1 *Dose Limiting Toxicity*

DLTs (see section 3.2.18) will be listed by study Part, cohort (part B only), radioactivity level adapted or not (part B only) and subject. Listings of AEs and abnormal laboratory values defined as DLTs will be also provided sorted by study Part, cohort (part B only), radioactivity level adapted or not (part B only) and subject.

A summary of DLTs will be provided, presenting the number of subjects with DLTs, the number of DLTs and the number of DTLs per type of DLTs (presented by decreasing frequency), by study Part, cohort (part B only), radioactivity level adapted or not (part B only) and overall.

3.2.1.2 Adverse events

All AEs will be recorded and graded by investigators using the NCI CTCAE classification v5.0 and will be coded using the Medical Dictionary for Regulatory Activities (MedDRA) Version 21.1 or higher and will be classified by MedDRA preferred term and system organ class.

Listings will be presented and sorted by study part, cohort (part B only), radioactivity level adapted or not (part B only), subject number, start time of AEs, primary system organ class, preferred term and verbatim text for all adverse events recorded during the study.

Listings of all adverse events, serious adverse events (SAE), adverse events leading to withdrawal, adverse events leading to dose reduction, adverse events leading to dose interruption, adverse events leading to dose delayed, adverse events with CTCAE Grade 3,4 and 5 and listings of deaths will also be presented.

Treatment Emergent Adverse Events (TEAE) will be flagged (*) in the adverse events listing and will be summarised.

A TEAE is defined as any adverse event that occurs up to 6 months (180 days) post last dose if:

- (1) it was not present prior to receiving the first dose of IRPP (or OPS301 if applicable), taking into account the time of administration and the time of AE, or
- (2) it was present prior to receiving the first dose of IRPP (or OPS301 if applicable) but the intensity/grade increased during the active phase of the study, taking into account the time of administration and the time of AE, or
- (3) it was present prior to receiving the first dose of IRPP (or OPS301 if applicable), the intensity/grade is the same but the causality changed to “related” during the active phase of the study, taking into account the time of administration and the time of AE.

Phase of the study will be defined into 3 time periods:

- period 1: treatment intake up to 56 days/8 weeks (corresponding to 8 half-lives of the ¹⁷⁷Lutetium rounded to the upper number of weeks, 162 hours * 8 + 2 days) after last dose
- period 2: 57 days up to 6 months post last dose
- period 3: after 6 months of last dose until 2-year follow-up period /death or lost to follow-up

An overall summary table (by period 1, 2 and 1+2) of all treatment emergent adverse events will be presented by study part, cohort (part B only) and overall using the Safety Analysis Set. This table will be also repeated for period 3.

All AEs and SAEs occurring during the Screening period and more than 6 months after the last dose of study medication will be listed and flagged as occurring before or after (during period 3) the active phase of the study; however, these will not be defined as TEAEs.

TEAEs will be summarised by study part, cohort (part B only) and overall with the number and percentage of subjects with adverse events classified by primary system organ class and preferred term. The number of occurrences of a TEAE will also be presented. The summary of AEs will also be repeated by time period. A listing of AEs by time period will also be presented.

In addition, summary tables will also be presented for SAEs, TEAEs related to ¹⁷⁷Lu-OPS201, TEAEs related to OPS301, treatment emergent ¹⁷⁷Lu-OPS201 related SAEs, OPS301 related SAEs, TEAEs leading to premature discontinuation of study medication, TEAEs leading to dose delays, TEAEs leading to dose reduction, TEAEs leading to dose interruption, TEAEs per decreasing frequency, TEAEs by associated NCI CTC worst grade and by causality. There will also be a separate summary for Adverse Events of Special Interest (AESI) which will be defined as any TEAE related to ¹⁷⁷Lu-OPS201 which occurs the day of ¹⁷⁷Lu-OPS201 administration (same date as ¹⁷⁷Lu-OPS201 administration and at any cycle).

Summary tables of adverse events will be provided with the number and percentage of subjects with adverse events classified by primary system organ class, preferred term (ordered alphabetically) and associated CTCAE version 5.0 worst grade. In the event of multiple occurrences of the same adverse events being reported by the same subject, the maximum intensity (Grade 5 > Grade 4 > Grade 3 > Grade 2 > Grade 1 > missing > not applicable) and the most serious causality (related > not related) will be chosen.

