6.3.3 Antiemetic

[figure not shown]
To counteract the known side effects of this amino acid infusion, such as nausea, 8 mg dexamethasone (antiemetic) and as-required ondansetron (8 mg i.v.) will be administered 15 to 30 minutes before the start of the amino acid infusion (unless there are contraindications for these drugs). From adoption of the protocol version (v6.0), investigators are advised, if required, to control symptoms it is allowed to use antiemetic regime as per site's standard of care and to add extra antiemetic medication including short-term steroids (unless there are contraindications for these drugs). Any antiemetic drug administered to the subject must be documented in the eCRF.

6.3.4 *Optional: Loop Diuretic*

To facilitate the renal elimination of the radioactive peptide, 20 mg furosemide i.v. (loop diuretic) can be administered 30 to 60 minutes prior to the administration of the study medication. This is optional and can be decided by the investigator, but must be documented in the eCRF.

6.3.5 *Administration Scheme*

Figure 14 Administration Schedule for Study Treatment and Concomitant Medication

i.v.=intravenous.

0 h=end of infusion.

Antiemetic and loop diuretic are administered if required.

¹⁷⁷Lu-OPS201 infusion takes place over 120 minutes (see Section 6.2.1).

6.3.6 *Prior and Further Concomitant Treatments*

Subjects will be excluded from the study if they have received any other IRPP. Therapy given subsequently to study medication needs to be considered carefully: if radionuclide therapy is used, the prior radiation doses to the normal tissues need to be considered; and any therapy (such as chemotherapy or radionuclide therapy) should not be started until it is clear that the subject has recovered sufficiently from the adverse events associated with study medication.

During the study period other concomitant medications are permitted at the discretion of the investigator. With the exception of the therapeutic use of SSAs (see Section 6.3.1), NET-specific treatments are not allowed until the end of the core study. In case the investigator considers a NET-specific treatment is deemed necessary for the benefit and well-being of the subject, they should withdraw the subject from study treatment and perform the Withdrawal visit as specified in Section 5.

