8.1.4.1 Reporting of Adverse Events

Any AE/SAE occurring during the study, from informed consent up to 6 months after last study drug administration, must be reported to the sponsor.

Up to 6 months after the last study drug administration, all AEs/SAEs will be collected unless NET therapies are started, then only AEs/SAEs considered by the investigator to be related to the study drug/procedure will be collected. From 6 months after the last study drug administration until 2 years after the EOCT/EOAC/EW Visit, withdrawal of consent, lost to follow-up or death, all AEs/SAEs related to the study drug/procedure will be collected.

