2.2 Safety

The Safety Analysis Set (SAS) will consist of all subjects who received study medication.

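### By-period adverse event percentages keep every dosed subject in the denominator, including those no longer under full AE collection, so Period 2 all-causality rates are biased down and Period 2 and 3 rates are diluted by loss to follow-up and consent withdrawal

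*SAP*

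**What the plan says.** SAP 3.2.1.2 defines Period 1 as up to 56 days after the last dose, Period 2 as day 57 to 6 months, and Period 3 as the time after that to the end of the 2-year follow-up, death or loss. The overview is specified as follows: "An overall summary table (by period 1, 2 and 1+2) of all treatment emergent adverse events will be presented". The population and the third period come next: "overall using the Safety Analysis Set. This table will be also repeated for period 3". The table of subjects with events by system organ class and preferred term follows the same split: "The summary of AEs will also be repeated by time period".

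SAP 3.2.1 sets the general rule that "summary tables will be based on the Safety Analysis Set", and SAP 2.2 defines that set: "The Safety Analysis Set (SAS) will consist of all subjects who received study medication". Membership does not depend on reaching a later period or being observed in it.

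Protocol 8.1.4.1 governs what is recorded: "Up to 6 months after the last study drug administration, all AEs/SAEs will be collected unless NET therapies are started". After such a start, only events judged related to study drug or procedure are collected. Beyond 6 months, only related events are collected for every subject. Collection stops 2 years after the end-of-treatment visit, or earlier at consent withdrawal, loss to follow-up or death. Protocol 6.3.6 adds that, somatostatin analogues aside, "NET-specific treatments are not allowed until the end of the core study"; a subject who needs such treatment sooner is withdrawn from study treatment.

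**The concern.** The denominator and the collection rule do not match. A subject who starts another NET therapy on day 60 after the last dose has no unrelated events recorded from then to day 180, yet the Period 2 table counts that subject as event-free for unrelated events. A subject lost or withdrawn before Period 3 counts as event-free throughout it. SAP 3.2.1.2 gives no at-risk number per period, no censoring rule and no rate per subject-time.

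Safety is the primary objective, and Protocol 1.3.6.2 expects delayed reactions, so the later periods will be read closely. The reasons for non-observation (new therapy, death, dropout) are plausibly linked to treatment failure, so dilution may differ between cohorts. Most Part B cohorts enrol three to five subjects, where one change in the denominator is visible.

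**Working it through.** **Period limits.** The plan's one figure here reproduces: 162 h × 8 / 24 + 2 d = 54 + 2 = 56 days. Period 2 therefore lasts 180 − 56 = 124 days. If the end-of-treatment visit falls 56 days after the last dose, Period 3 lasts 56 + 730 − 180 = 606 days.

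**Who is observed for what.**

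| Status | Period 2, unrelated AEs | Period 2, related AEs | Period 3, related AEs | In denominator |
|---|---|---|---|---|
| In follow-up, no new NET therapy | yes | yes | yes | yes |
| In follow-up, new NET therapy started | no | yes | yes | yes |
| Lost or consent withdrawn | no | no | no | yes |
| Died | no | no | no | yes |
| Stopped study treatment only | yes | yes | yes | yes |

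Unrelated events are collected for nobody in Period 3. The last row follows from Protocol 4.6.1 and 6.4: the early withdrawal visit and long-term follow-up still take place.

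**Size: inputs.** The documents give neither the fraction f unobserved nor the risk p among observed subjects. I assume f from 10% to 50% and p of 10% or 20%, and that unobserved subjects have the same underlying risk.

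*(a) Unobserved from the start of the period:* reported = (1 − f) × p.

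*(b) Exits spread evenly over the period, constant hazard h = −ln(1 − p):* reported = (1 − f)p + f[1 − (1 − e^(−h))/h]. For p = 20%, h = 0.223 and the bracket is 10.4%. For p = 10%, h = 0.105 and the bracket is 5.1%.

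| f | p = 20%, (a) | p = 20%, (b) | p = 10%, (a) | p = 10%, (b) |
|---|---|---|---|---|
| 10% | 18.0% | 19.0% | 9.0% | 9.5% |
| 20% | 16.0% | 18.1% | 8.0% | 9.0% |
| 30% | 14.0% | 17.1% | 7.0% | 8.5% |
| 50% | 10.0% | 15.2% | 5.0% | 7.5% |

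In (a) the relative understatement equals f; in (b) it is about half of f.

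**Related events after a switch.** These are still collected, which shrinks the effect of new therapy. Assume a true Period 2 risk of 50%, so λ = ln 2 / 124 = 0.00559 per day. Let s = 20% of subjects switch at a time u spread evenly over the first 63 days of the period, and let a share r of the hazard be judged related. Reported = (1 − s)p + s × mean[1 − exp(−λu − rλ(124 − u))].

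- r = 0: 0.8 × 50% + 0.2 × 15.7% = 43.1%, a relative loss of 14%.
- r = 0.5: 0.8 × 50% + 0.2 × 35.2% = 47.0%, a relative loss of 6%.
- r = 1: no loss.

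**In counts (illustrative).** Four subjects with an event give 4/40 = 10.0% of all dosed, against 4/30 = 13.3% of those still observed. In a five-subject cohort, 1/5 = 20.0% against 1/3 = 33.3%.

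**The case against.** A reader might infer that new NET therapy hides the delayed renal and marrow toxicity that matters most. The documents do not support that. Events judged related are still collected after a switch, and dose limiting toxicities are related by definition (Protocol 3.8), so this rule loses such an event only if it is attributed elsewhere. Haematology and biochemistry also continue at the long-term follow-up visits (Protocol 5.2.9), and SAP 3.2.1.3 plans shift tables, Grade 3 and 4 listings and listings of low eGFR. This stands, and it limits the harm to all-causality percentages and to losses from follow-up.

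A reader might also extend the new-therapy problem to Period 3. It does not reach there, because Period 3 is related-only for everyone. For deaths, a full-set percentage is a legitimate cumulative incidence with death as a competing event, provided it is labelled as one. Both corrections stand.

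SAP 3.2.15 sets a general denominator of non-missing observations and allows a footnote. It does not settle the matter: the absence of an AE record is not a missing value, and the SAP does not say what a non-missing observation would be for an AE period. At best the denominator is undefined.

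Finally, attrition is visible elsewhere. SAP 3.2.5 and 3.2.6 tabulate subjects at each assessment and withdrawals with reasons, and SAP 3.2.1.2 already has a related-event table and a listing by period. A careful reader could piece together part of the picture, but the period percentages would still be printed on the wrong base.

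**Conclusion.** The point holds in limited form. Followed as written, the plan biases Period 2 all-causality percentages downward and dilutes Period 2 and Period 3 percentages through loss to follow-up and consent withdrawal. The direction is clear; the size is not computable from the documents. At equal underlying risk, the relative understatement is bounded by the fraction unobserved, and is smaller where exits fall within the period or events are judged related. If unobserved subjects were at higher risk, that bound would not hold against the risk in all dosed subjects.

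A reader might be tempted to state a specific loss by treating the 3 of 19 subjects with progression in the investigator study (Protocol 1.4) as a switching rate, or by assuming that switching clusters around day 56. Neither is supported. That share is progression in a different trial, and Protocol 6.3.6 gives a restriction, not observed timing.

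This is a cheap improvement to a descriptive safety analysis. It does not show that late toxicity will be missed.

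**What to change.** Amend SAP 3.2.1.2:

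1. For Periods 2 and 3, use as denominator, and display by part and cohort, the number of subjects alive and under AE follow-up at the start of the period. Where a full-set percentage is kept, label it a cumulative incidence with death as a competing event.
2. In the Period 2 all-causality table, leave out of the denominator subjects who started a new NET therapy before Period 2. In the Period 2 and 1+2 all-causality tables, stop counting at the start of new NET therapy and show how many subjects were censored. Those who switch mid-period still dilute a simple percentage; events per subject-time observed would deal with that and is optional.
3. Run the existing related-event table over the full period without that censoring. Title the Period 3 table as related AEs only and not as TEAEs: the TEAE definition stops at 180 days, and the same section says later events are not TEAEs, yet it repeats the TEAE overview for Period 3.

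Cost: SAP wording and a few extra columns, with denominators that differ between periods and need a footnote. Subsequent NET treatments, survival and withdrawals are already recorded, so no new data are needed.

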3.2.1.3 Laboratory data

A separate listing of normal ranges for SI and local laboratories units will be provided by study site laboratory, gender and age where relevant.

Laboratory data (including hematology, biochemistry, pituitary markers and urinalysis) will be listed in SI and local laboratories units and abnormal values will be flagged (High, [H], Low [L], clinically significant [C], CTCAE version 5.0 grade (G)) where applicable. Any unscheduled laboratory assessments will be flagged [U] in the listings. In addition, a listing of clinically significant abnormal values will be presented.

As multiple local laboratories are used within the study, a data normalisation method (refer to [Appendix 1: Derived Data](#), and Ref. 5, 6, 7) will be used before summarising the data. The normalized lab data values will be also included in the lab data listings together with the reference normal range limits used for the normalisation.

(a) Hematology, Biochemistry and Pituitary Markers

For hematology, biochemistry and pituitary marker parameters, the baseline will be defined as the last measurement collected prior to the first dose of study drug.

For hematology, biochemistry and pituitary marker parameters, summary statistics, by study part, cohort (part B only) and overall, will be presented at each scheduled assessment for normalised actual values and changes from baseline. For pituitary markers, all values will be displayed in a listing, however the summary tables may exclude any results if it was drawn while the subject was receiving medication that may have been deemed to impact the result.

The determination of the medications impacting the result will be based upon medical monitor review and reflected in a footnote.

Shift tables from Baseline to worst post-baseline and also, each post baseline visit. In the shift tables, the number and percentages of subjects with low, normal, or high values will be presented by study part, cohort (part B only) and overall.

For hematology and biochemistry, summary statistics by study part, cohort (part B only) and overall, will be also provided for nadir and day to nadir by cycle (time from cycle baseline to nadir during the same cycle) and on lab toxicities after start of study medication with worst CTCAE version 5.0 Grades 3 and 4 (refer to Appendix 1, Derived data).

Shift tables from Baseline to worst CTCAE version 5.0 Grade of hemoglobin, absolute neutrophil count, and platelet count, will be presented by study part, cohort (part B only) and overall.

Hematological and biochemistry toxicities will be recorded and graded according to the CTCAE criteria, Version 5.0. The CTCAE grade (0 to 4) of hematology and biochemistry by cycle and by subject will be listed in the Section 16.2.8. Listings of the laboratory parameters in section 14.3.4 will include a listing of all CTCAE Grade 3 and 4 hematological toxicities, a listing of CTCAE Grade 3 and 4 hematological toxicities lasting 4 weeks or more, a listing of CTCAE Grade 2 hematological toxicities lasting 4 weeks or more, a listing of all CTCAE Grade 3 and 4 biochemical toxicities, a listing of CTCAE Grade 3 and 4 biochemical toxicities lasting 4 weeks or more, a listing of CTCAE Grade 2 biochemical toxicities lasting 4 weeks or more, a listing of all eGFR of < 45mL/min, a listing of eGFR of < 45mL/min lasting 4 weeks or more, a listing of out of range biochemistry parameters that could not be graded using CTCAE grade (below LLN – normal – above ULN) and a listing of biochemistry parameters that could not be graded using CTCAE grade (below LLN – normal – above ULN) lasting 4 weeks or more.

In addition, figures of absolute leucocyte count, absolute neutrophil count, absolute lymphocyte count, platelet count, hemoglobin, AST, ALT, AP, total bilirubin, creatinine, eGFR individual normalised values over time will be displayed.

(b) Urinalysis

For categorical urinalysis data (absent/trace/positive and normal/abnormal) frequency tables, by study part, cohort (part B only) and overall, will be presented at each scheduled assessment as well as the change from baseline with the following categories: improved, stable, worsened and abnormal worsening.

Shift tables from Baseline to each post baseline visit for the number and percentage of subjects with normal, abnormal clinical evaluation will be presented by study part, cohort (part B only) and overall.

For continuous urinalysis data (specific gravity, PH), summary statistics, by study part, cohort (part B only) and overall, will be presented at each scheduled assessment for actual values and changes from baseline.

3.2.1.4 *Vital signs, weight and height*

Vital signs (supine blood pressure, supine heart rate, body temperature, body weight, BMI and BSA) will be listed at each assessment by study part, cohort (part B only), radioactivity level adapted or not (part B only) and subject. Any unscheduled vital signs assessment will be flagged [U] in the listing.

Baseline values will be defined as the last vital signs measurement collected prior to the first dose of study drug.

Summary statistics (n, mean, standard deviation, median, minimum and maximum) for supine blood pressure, supine heart rate, body weight, BMI and BSA by study part, cohort (part B only) and overall, will be presented at each scheduled assessment for actual values and changes from baseline.

3.2.1.5 *ECG*

Descriptive summaries of the following ECG and Holter parameters will be calculated: heart rate, RR interval, PR interval, QRS interval, QT interval, QTcB, and QTcF. The number and percentage of subjects with normal, abnormal (not clinically significant), abnormal (clinically significant) findings will be presented for patients in the Safety Analysis Set.

3.2.1.6 *Physical Examination*

Physical examination results (Normal / Abnormal) will be listed at each assessment by study part, cohort (part B only), radioactivity level adapted or not (part B only) and subject. Any unscheduled physical examination will be flagged [U] in the listings.

3.2.1.7 *Extent of Exposure*

The extent of study treatment exposure will be summarized by cohort, part and overall within the safety population.

The overall study treatment exposure will be summarized by:

- the number of cycles,
- actual cumulative dose defined as the sum of all doses of 177luOPS201 from the first dose to the last one. If one administered radioactivity dose is missing, the cumulative dose will not be calculated and will be set to missing.
- actual cumulative dose by cycle defined as the sum of all doses taken until the cycle presented. If one administered radioactivity dose is missing, the cumulative dose will not be calculated and will be set to missing
- duration of exposure (defined in section 7.1)
- overall study duration (defined in section 7.1)
- number of patients with OPS301 at any cycles

3.2.1.8 *Performance status (Karnofsky scoring)*

The performance status of the subjects as defined by the Karnofsky scoring:

- 100 - Normal; no complaints; no evidence of disease.
- 90 - Able to carry on normal activity; minor signs or symptoms of disease.

- 80 - Normal activity with effort; some signs or symptoms of disease.
- 70 - Cares for self; unable to carry on normal activity or to do active work.
- 60 - Requires occasional assistance, but is able to care for most of his personal needs.
- 50 - Requires considerable assistance and frequent medical care.
- 40 - Disabled; requires special care and assistance.
- 30 - Severely disabled; hospital admission is indicated although death not imminent.
- 20 - Very sick; hospital admission necessary; active supportive treatment necessary.
- 10 - Moribund; fatal processes progressing rapidly.
- 0 – Dead

Karnofsky performance status score will be analysed as quantitative variable and qualitative variable.

For Karnofsky performance status score as quantitative variable, descriptive statistics and 95% Confidence Interval (CI) of the mean will be presented for the raw data and for the changes from baseline during treatment, by study part, cohort (part B only) and overall at each visit (Visit 1, 2, 3 and EOCT Visit).

For Karnofsky performance status score as qualitative variable (class), the number and percentage of subjects per score level and per level of change from baseline, summarized as Worsening, No change and Improvement, will be provided by study part, cohort (part B only) and overall at each visit (Visit 1, 2, 3 and EOCT Visit). The shift from baseline at each visit will be also provided.

